Families' participation in the VUP and selection into cPW and ePW is determined by governmental policies and was not under the control of the research team. Lists of families participating in the VUP program were obtained from government staff in each district.

Nonoverlapping, geographically defined clusters were created comprising at least 30 families participating in the cPW program or ten families participating in the ePW program, with some clusters containing both ≥ 30 cPW and ≥ 10 ePW households. Clusters were formed from one or more contiguous villages such that one CBV could provide services to all participating families in the cluster. Villages within the same cluster were selected to be as close to each other and as far apart from other clusters as possible. Due to the relative scarcity of the ePW families, 100% of clusters containing at least 10 ePW families were sampled for participation in the study. Clusters which contained cPW families (including combined clusters containing ePW families) were randomly sampled for inclusion into our study until we reached our target sample size of $\geq 1,040$ households. Randomization was performed by Laterite and occurred at the cluster level within strata defined by public works type (ePW only, combined ePW/cPW, and cPW only) and

geographic sector. Within strata, clusters were assigned random numbers and placed on a ranked list. The first half of clusters on the randomly ranked list were assigned to treatment. In case of an uneven number of clusters per strata, a lottery was used to round the number assigned to treatment up or down. After assignment of the cluster, households were contacted by the data collection contractor and invited to participate in the study. Clusters were retained if at least five families in the cPW strata or at least one family in the ePW strata enrolled and had at least one child aged 6–36 months. We retained 48 ePW-only clusters, 38 ePW/cPW clusters, and 112 cPW-only clusters (Cluster sampling strategy, Figure 2).

Neither the families nor the enumerators who conducted the assessments knew about a family’s assignment to treatment versus control before they had completed the baseline assessment. All caregivers gave written informed consent for themselves and their eligible children ages 6–36 months.

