ePW = expanded public works; cPW = classic public works; ¹Clusters had to include ≥ 10 ePW households to be eligible as an ePW cluster; ²Cluster had to include ≥ 30 ePW households to be eligible as a cPW cluster; ³Randomization within strata of Public Works x Sector did not necessarily guarantee even numbers in the treatment and control arms

Figure 2. Cluster sampling strategy and flow Chart of Participants in the *Sugira Muryango* Open Trial.

Note: Although each cluster had a 50% chance of being assigned to receive treatment, we were not guaranteed an equal number of treatment and control clusters because randomization occurred within relatively small strata that sometimes contained an odd number of clusters.

Study Visits

Data collection occurs at three timepoints referred to as baseline, midline (4 months post intervention) and endline (12 months after midline). All assessments are carried out in the homes of the families or at a central point in the village.

At each time point, the caregiver who states that he or she knows the child best—most often the biological mother—provides reports on child development, health, feeding practices. This “primary caregiver” also participates in the assessment of caregiver-child interactions and provides information about the household including family composition, economic status, household assets, social protection, and finances. Both the primary caregiver, their intimate partner or other secondary caregivers living in the households (e.g. grandparents, adoptive parents, aunts and uncles) respond to a battery of questionnaires that cover aspects of caregiver mental health, trauma exposures, daily hardships, family functioning, decision making, alcohol consumption, and intimate partner violence. Measures were drawn from previous pilot and research studies in Rwanda (Betancourt et al. 2018) and followed a rigorous translation protocol, including forward- and back-translation from English to Kinyarwanda.

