mixed effect model with a MDAT subscale, for example, as the response variable and the primary predictors are treatment group (SM vs CG), time and their two-way interaction included as fixed effects. Mixed effect models also known as hierarchical linear models (HLM) or multi-level models are a flexible tool for analyzing associations and changes over time in longitudinal studies when there are clusters of correlated data in the outcome variable. This design has three levels of nesting, families are measured within measurement waves, and measurement waves are nested within randomization cluster or region. Since, we expect region and time level effects subject-specific slopes and intercepts will be modeled as random effects nested within randomization cluster also modeled as a random effect. Additionally, there may be due to VUP program (recall we stratify the randomization of clusters within public works cluster). Type of VUP program will be model as a fixed effect. A mathematical representation of this model is:

$$Y_{ijkm} = B_0 + b_{0i} + B_1 * TreatmentGroup + B_2 * Time + b_{1i} * Time + B_3 * Time * Treatment group + b_{2k} + b_{3k} * time + B_{4m} * PubicWorksGroup + e$$

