Where, Y_{ijkm} represents the value of the i th family ($i = 1 \dots I$), at the j th time point ($j=1, \dots 3$), in the k th cluster ($k = 1, \dots 200$) and m is the VUP indicator with levels expanded public works, classic public works and mixed. The set of b_{0i} variables represent subject-specific intercepts and are assumed $b_{0i} \sim N(0, \sigma_i)$. The b_{1i} are subject specific slopes and assumed $b_{1i} \sim N(0, \sigma_{slopes})$, the b_{2k} are randomization cluster intercepts and assumed $b_{2k} \sim N(0, \sigma_{region})$ and the b_{3k} are region specific slopes and assumed $b_{3k} \sim N(0, \sigma_{sregion})$. The value e represents residual variation and is assumed $e \sim N(0, \sigma)$. Efficacy will be based on the likelihood ratio test for inclusion of the Time*Treatment interaction (null hypothesis $B_3 = 0$). Random effects will be subject to a limited amount of model building as we would like to simplify the model where appropriate. For example, we would want to test if we can assume a common cluster slope versus a unique slope for each cluster. Cluster and subject-specific effects will be dropped from the model based on a Likelihood Ratio Test (LRT) for their inclusion. The estimation procedure while model building random effects will be Restricted Maximum Likelihood (REML). The primary hypothesis test which is based on the inclusion of a fixed effect will require models estimated by maximum likelihood. Because of randomization we have controlled in theory for all variables observed and unobserved, however treatment group imbalance may still be present. We explore treatment group characteristics for in-balance. However, previous work has showed baseline differences to be minimal.

Model assumptions and alternative tactics: Model assumptions will be verified. In particular we will examine the distributions of the residuals to verify that normality assumptions hold. Residual plots will reveal violations of the normality assumptions. Panel plots will be examined to look at functional shape assumptions within subject. In the case of non-normality of outcomes, we will consider response transformations or the use of models that do not require the normality assumptions including the class of generalized linear mixed effect models. If the linearity

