assumption does not hold across time (baseline, 3 months, and 12 months) we can treat time as a categorical variable to examine differences between the treatment groups at individual time points focusing on the 12-month group differences adjusted for baseline. If examination of panel plots reveals a large amount of heterogeneity among trajectories of the outcomes by subjects we can use Growth Mixture Models which first identify clusters of similar trajectories from which we can test for treatment group differences in terms of membership in the clusters of similar trajectories.

Outliers will be flagged through visual inspection and standardized residual values greater than 3. A sensitivity analysis will be done to determine if outlier removal changes the coefficient values. If we find that outliers are having an oversized effect on the estimated coefficient values we will give preference to the models where the outliers are removed. However, we will present both results.

Some responses are scales or derivations of scales in particular the MDAT and the ASQ. We will examine the psychometric performance of these scales. We are especially concerned with internal consistency and item reliability. If these scales do not show at a minimal amount of internal consistency (Cronbach's Alpha > 0.6) these items will not be considered for analysis. If particular items are an issue they may be dropped from the scale. Research, in areas like Rwanda suffer because standard scales have not been validated on these populations.

Binary Outcome ASQ, shared decision making, father engagement: The analysis for these outcomes will be similar to the analyses above with accommodations being made for the fact the ASQ is a binary outcome. In particular, we will have to make use of mixed effect logistic regression models a form of generalized linear mixed models (GLMM) with a binomial distribution and a logistic link. Outside of accounting for the correct distribution of the response variable the analysis will follow the methods outlined in the previous MDAT section.

Model Assumptions and Alternative Tactics: We will examine Pearson residuals to assess goodness of fit. Alternative methods include the use of quasi-binomial mixed effects regression (in the case of over dispersion). However, such models do not have a full likelihood and instead of LRT test we will have to rely on the Wald-type type test for regression coefficients.

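### Clusters were randomised within public works type by sector, but the Time x Treatment test is in effect unadjusted for either factor; the cost is modest power, not bias

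*Combined protocol and SAP*

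**What the plan says.** **Design.** Section B, Randomization Plan, randomises clusters within strata formed by crossing three public works categories with a second factor: "geographic sector. Within strata, clusters were assigned random numbers and placed on a ranked list". Half of each list went to treatment, with a lottery for odd numbers. The Figure 2 note adds that "randomization occurred within relatively small strata that sometimes contained an odd number of clusters".

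**Analysis.** Section D, Data Analysis Plan, Continuous Outcomes, mentions only the first stratifier ("recall we stratify the randomization of clusters within public works cluster") and states: "Type of VUP program will be model as a fixed effect". The model definition adds that "m is the VUP indicator with levels expanded public works, classic public works and mixed". The equation contains treatment, time, their interaction (B3), family intercepts and slopes, cluster intercepts and slopes (b_2k, b_3k), and public works without a time term. The word region appears in the text and in the variance labels, but those terms carry the cluster index k = 1 to 200, so they are not a sector effect. Sector is absent from the equation, from the design variables in Table 2 and from the listed inputs under Power and Sample Size.

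**Test.** Efficacy is the likelihood ratio test (LRT) of B3 = 0. Random effects may be removed first: "Cluster and subject-specific effects will be dropped from the model based on a Likelihood Ratio Test (LRT) for their inclusion". The binary and zero-inflated Poisson analyses take over the same structure.

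**The concern.** Stratified allocation balances the arms on anything the strata predict. If strata predict change over time, that balance removes part of the cluster-level variation from the true sampling error of B3. A model without stratum x time terms still counts that variation as noise in b_3k. The reported standard error is then too large, the test falls below its nominal 5%, and part of the precision that the design provides is not used.

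The public works main effect does not repair this. It shifts the level at all three waves equally, while B3 concerns the difference in slopes. The plan expects change to vary by area, since it gives each cluster its own slope, but it never lets the second stratifier carry any of that variation.

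Power is at stake, not validity of the estimate. The conservative direction also depends on b_3k staying in the model, which the plan does not guarantee.

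**Working it through.** **Inputs from the documents.** 200 clusters of 5 families, ICC 0.10, SD 1, alpha 0.05, effect sizes 0.22 and 0.25 (Power and Sample Size). Retained clusters: 48 + 38 + 112 = 198, with a target of at least 1,040 households (Randomization Plan). Waves at 0, 4 and 16 months (Data Analysis Plan).

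**Assumptions not in the documents.** 20, 30 or 40 sectors. Sector share R of the cluster-level variance in change: 0, 25, 50 or 75%. ICC of change 0.10, 0.05 or 0.02, because the plan does not say to which scale its 0.10 applies.

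**Step 1: the plan's own power.** Design effect = 1 + (5 - 1) x 0.10 = 1.4. Effective size per arm = 500 / 1.4 = 357.1. SE = sqrt(2 / 357.1) = 0.0748. Power at 0.22 = Phi(0.22 / 0.0748 - 1.96) = 83.6%; at 0.25, 91.6%. Both agree with the stated floors of 80% and 90%, without loss to follow-up.

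**Step 2: does the public works main effect adjust B3?** In a generalised least squares check (198 clusters x 5 families x 3 waves), putting the term in or leaving it out moved B3 by 0 with complete data, and by a mean of 0.007-0.010 SE with 10-20% of follow-up values missing. It does not adjust the test.

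**Step 3: closed form with perfect balance.** The fraction of the variance of a cluster mean slope that strata explain is f = R x 0.10 / (0.10 + 0.90 / 5). At R = 50%, f = 0.05 / 0.28 = 0.179 and sqrt(1 - f) = 0.906.
- Type I error as planned: 2[1 - Phi(1.96 / 0.906)] = 3.1%.
- Power at 0.22 as planned: Phi((0.22 / 0.0748 - 1.96) / 0.906) = 86.0%.
- Power at 0.22 with strata x time modelled: Phi(0.22 / (0.0748 x 0.906) - 1.96) = 90.0%.

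The gain is 4.0 points at best, because odd strata and extra parameters are ignored here.

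**Step 4: simulation with the actual allocation rule.** 198 clusters (148 of 5 and 50 of 6 families), half of each stratum to treatment, lottery for odd strata, about 50-85 strata. Maximum-likelihood LRT with b_3k kept; alternative model with public works x time fixed and sector random. ICC 0.10, effect 0.22, 16,000 runs per cell; ranges run over 20-40 sectors. Power for the alternative is at a true 5% level.

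| Sector share | Plan SE too large by | Plan type I error (%) | Plan power (%) | Power with strata modelled (%) | Net (points) |
|---|---|---|---|---|---|
| 0 | none (0-2% too small) | 5.1-5.5 | 83.8-84.1 | 82.5-83.7 | -1.3 to -0.4 |
| 25% | 3% | 4.3-4.6 | 85.2-85.3 | 86.2-86.6 | +1.0 to +1.3 |
| 50% | 6-7% | 3.6-3.8 | 85.9-86.6 | 89.0-90.0 | +3.1 to +3.4 |
| 75% | 12% | 2.8-2.9 | 87.0-87.6 | 92.8-92.9 | +5.2 to +5.9 |

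Monte Carlo error is about 0.3 points on a power and 0.5 on a net change. For shares of 0 / 25 / 50 / 75%, the net change at ICC 0.05 is -0.5 to +0.1 / 0.0 to +0.9 / +1.2 to +1.5 / +1.8 to +2.3 points. At ICC 0.02 it is -0.4 to +0.1 / 0.0 to +0.4 / +0.2 to +0.3 / +0.5 to +0.6 points.

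A separate simulation with the ordinary LRT cutoff (30 sectors, ICC 0.10, error about 0.6 points) gave plan against alternative power of 82.7 v 83.2% at share 0, 84.1 v 86.1% at 25% and 85.8 v 89.3% at 50%. With public works alone explaining 25%, power moved from 84.0 to 86.8%.

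**Step 5: loss to follow-up.** If 20% of families are lost (assumed; complete-case approximation), 832 families remain and step 1 gives 78.9% at 0.22 and 88.1% at 0.25. Simulated power at 0.22 with 30 sectors, plan to alternative, for the four shares: 79.0 to 78.9, 79.7 to 80.3, 80.1 to 83.3 and 81.5 to 86.9%.

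**Step 6: if b_3k is dropped.** If it is always dropped at ICC 0.10, type I error is 10.1-10.4 / 8.9-9.1 / 7.7-8.1 / 6.1-6.5% for the four shares. With the plan's drop rule applied at an assumed 5% level, the slope goes in 2-6% of runs at ICC 0.10, 41-45% at 0.05 (overall type I error 4.3-5.8%) and 85-86% at 0.02 (4.6-5.7%).

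**Step 7: can the alternative be fitted?** In a three-wave model with complete data, 30 sectors and ICC 0.10, both models converged in 300 of 300 datasets at share 0 and at share 50%. Plan SE / alternative SE was 1.009 and 1.093. The sector slope variance was estimated at zero in 61% of datasets at share 0 and in 1% at share 50%.

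**The case against.** The strongest case against is materiality. Nothing in the documents shows that strata predict change, and the number of sectors is not given. Gains of 3 points or more need both an ICC of change of 0.10 and a sector share of at least half. At share 0 the change loses a little power. No stated figure fails because of the omission. All of this stands, and it is why the priority is low to moderate.

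The word conservative is fragile: at ICC 0.05 or 0.02 the plan's own drop rule often removes the cluster slope, and overall type I error then lies around 5%. This also stands. Dropping b_3k is a separate defect, and the shortfall under 20% loss comes from the assumed attrition, not from leaving out strata.

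Two objections do not stand. One is that public works x time has no demonstrated effect; a 25% public works share alone raised power by 86.8 - 84.0 = 2.8 points. The other is that the power comparison is uneven because only the alternative was recalibrated to a true 5% level; that recalibration works against the alternative, and the ordinary cutoff gives similar gains.

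Two limits remain. Of the 17 outcomes in Table 2, 9 are binary or counts, for which neither the size nor convergence was examined; the plan itself foresees numerical difficulty there. And the document is dated October 2019, after midline training in August 2018, so a change to the primary model may come after data have been seen.

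**Conclusion.** The concern holds. The linear-time efficacy test ignores sector and, for practical purposes, public works type, although clusters were randomised within both. This is a loss of efficiency, not a bias, and it does not by itself overturn the stated power.

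At effect size 0.22 and ICC 0.10, modelling the strata changes power by between -1.3 and +5.9 points as the assumed sector share runs from 0 to 75%; at ICC 0.05 the range is -0.5 to +2.3, and at 0.02 it is -0.4 to +0.6. The conservative type I error (down to 2.8%) requires that strata predict change and that b_3k is kept.

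The scope is the linear-time model. If the categorical-time fallback ("focusing on the 12-month group differences adjusted for baseline") is fitted as endline adjusted for baseline, the public works main effect does adjust the contrast, and only sector is missing. Confidence in the size is medium, because it rests on the assumed sector number, share and ICC.

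**What to change.** In the continuous-outcome model, pre-specify the three-level public works stratum x time as fixed effects, and sector as a random level above cluster with its own intercept and time effect. Keep the cluster and sector slopes in the primary test instead of dropping them by LRT. Add sector to the design variables in Table 2, and state that the three-level cluster stratum differs from the two-level household VUP status listed there.

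Do not use fixed effects for every public works x sector stratum by time: at ICC 0.10 the LRT then runs at 8.2-11.7%, and power at a true 5% level is 76.7-80.5%. Fixed sector x time alone gives 6.4-7.9% type I error.

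For the binary and zero-inflated Poisson models, include the same stratum terms and pre-specify a simpler form in case of non-convergence.

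The cost is SAP wording and a few parameters; sector is already known from randomisation. The downside is about 1 point of power if strata do not predict change (allow 2), and an LRT that may run slightly above 5% (4.9-5.7% at ICC 0.10, against 5.1-5.5% for the plan's model at share 0). If outcome data by arm have already been seen, report the adjusted model as a labelled sensitivity analysis.

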VUP-status [classic public works vs. expanded public works]	Government records
OUTCOME VARIABLES	
Malawi Developmental Assessment Tool (MDAT)	
Gross motor [standardized score]	MDAT
Fine motor [standardized score]	MDAT
Language [standardized score]	MDAT
Social [standardized score]	MDAT
Ages and Stages Questionnaire (ASQ-3)	
Gross motor [delayed/not delayed]	ASQ-3
Fine motor [delayed/not delayed]	ASQ-3
Communication [delayed/not delayed]	ASQ-3

Personal social [delayed/not delayed]	ASQ-3
Problem solving [delayed/not delayed]	ASQ-3
Anthropometrics	
Height-for-age (HAZ)	Anthropometrics
Weight-for-age (WAZ)	Anthropometrics
Weight-for-height (WHZ)	Anthropometrics
Middle upper arm circumference (MUAC)	Anthropometrics
"Father engagement "	
" father spends time every day caring for the child"	HOME
Family Violence	
Violent discipline [cumulative score, 0-7]	MICS-5 Hash discipline module
Intimate partner violence	
Victimization physical and sexual abuse past 3 months [cumulative score 0-7]*	Conflict Tactics Scale- CTS2
Perpetration physical and sexual abuse past 3 months [cumulative score 0-7]**	Conflict Tactics Scale- CTS2

*Among cohabitating or married mothers only

**Among cohabitating or married fathers only

***Among cohabitating or married caregivers only

Table 2. Study predictor and outcome variables.

Data Analysis Plan

Standard descriptive statistics will be used to describe the study sample. Frequencies and percentages will be reported for categorical variables and mean, median, standard deviation, interquartile range, maximum and minimum values will be reported for continuous variables. Anthropometric data will be cleaned for extreme out-of-range values. Scales will be created from individual items according to scoring instructions for each scale. All scales will be evaluated for psychometric properties. Visual inspection of histograms and other plots will be used to identify outliers.

Continuous Outcomes MDAT, WAZ, MUAC, WHZ: The goal is to determine the efficacy of SM at 12 months from study initiation. Measurements of all outcome variables (see Table 2 and Section B), are taken at baseline, midline (4 months post baseline), and endline (12 months post midline). Subjects are randomized (Section B) into a treatment group (SM) and CG. Effectiveness will be determined if the slope of the response variable for the SM group is significantly different than the slope of the CG group. To test this hypothesis, we will fit a linear

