In fitting logistic mixed effect regression models, it is possible that we may run into numerical difficulties in computing a likelihood ratio test, so score type tests may be needed. This is more likely to occur in the case of testing for variance components.

Count Outcomes, harsh discipline, physical and sexual violence: These metrics count types of harsh discipline action or physical and sexual abuse as suffered or inflicted. Our experience with these scales is that there are more values of zero than what would be predicted by a standard

Poisson distribution. Our analysis will make use of Zero Inflated Poisson (ZIP) models (Everitt, & Hothorn, 2005; Long, 1997). These models belong to the more general class of mixture models. In particular they model the binomial probability of a count of zero versus a count greater than zero and the Poisson probability for counts greater than zero. In particular we will fit mixed effect models as described in the continuous variable sections but under the ZIP distribution assumption.

A key difference between a mixture model and more standard probability distributions is the fixed effects structure and tests for significance can vary between the two parts (binomial and Poisson). Likelihood ratio testing for the Time*Treatment group interaction will be performed for both components of the mixture model. A significant result of the LRT test for the binomial portion would indicate that the probability of no violence (inflicted or suffered) differed between the treatment groups. A significant result of the LRT on the Poisson portion of the ZIP model would indicate that among those who inflicted or suffered harsh discipline or violence the mean amount of violence differed between the treatment groups. The two portions are contained in a single likelihood function and parameter estimation is done simultaneously.

Model Assumptions and Alternative Tactics: The key assumption in these models is the ZIP distribution of the response variables. We will visually inspect the distribution of the outcome variables to verify that we are fitting the correct model. Alternative distributions could be Poisson, Quasi-Poisson, Binomial (data dichotomized due to lack of variability), or Negative Binomial. These are non-mixture models and modeling will follow the process outlined in the continuous outcomes section.

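### The random effects of the randomised unit (the cluster) can be dropped on a non-significant likelihood ratio test; the inflation is small and a wording change removes it

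*Combined protocol and SAP*

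**What the plan says.** Allocation is by geographic cluster (section B, Randomization Plan), with 48 + 38 + 112 = 198 clusters retained. The model for continuous outcomes (section D, Data Analysis Plan) has a random intercept and slope for the family and a random intercept (b2k) and slope (b3k) for the cluster. Efficacy rests on a likelihood ratio test (LRT) of B3, the Time-by-Treatment term.

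The same paragraph then allows the random part to be simplified: "Cluster and subject-specific effects will be dropped from the model based on a Likelihood Ratio Test (LRT) for their inclusion". Its own example is that "we would want to test if we can assume a common cluster slope versus a unique slope for each cluster". It states no cut-off and no exception for the cluster.

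If change over time is not linear, the fallback makes time categorical, "focusing on the 12-month group differences adjusted for baseline". For binary outcomes, "the analysis will follow the methods outlined in the previous MDAT section". For counts the text reads: "In particular we will fit mixed effect models as described in the continuous variable sections but under the ZIP distribution assumption". The binary section also warns that "it is possible that we may run into numerical difficulties in computing a likelihood ratio test", chiefly for variance components, and offers score-type tests as the remedy.

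Power and Sample Size assumes 200 clusters of 5 families and an ICC of 0.10. It does not say whether that ICC refers to level or to change.

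**The concern.** Treatment varies only between clusters, so B3 has to be judged against the variation in slopes between clusters. In this model b3k carries that variation, and b3k is the term the plan offers as its example of one to test away. The cluster intercept matters mainly for the fallback comparison at 12 months.

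With about five families per cluster, a non-significant variance test is weak evidence that the variance is zero. If the term is removed when some variance is present, the standard error of B3 is too small and the type I error exceeds 5%. The rule also sits awkwardly with a sample size that presumes clustering.

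**Working it through.** **1. The plan's own power.** Inputs from Power and Sample Size: 500 families per arm, ICC 0.10, SD 1, alpha 0.05 (taken as two-sided). Design effect = 1 + (5 − 1) × 0.10 = 1.4, so the effective n per arm is 500/1.4 = 357. Power = Φ(d√(357/2) − 1.96). This gives 91.6% for d = 0.25 and 83.6% for d = 0.22, consistent with the stated at least 90% and at least 80%. The stated power therefore already assumes that clustering is modelled.

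**2. How often the LRT drops the cluster slope.** Treat each family's slope as one observation: 198 clusters × 5 families, two arms, no treatment effect. The degrees of freedom are 198 − 2 = 196 between clusters and 198 × 4 = 792 within. With F the ratio of the between to the within mean square, the REML statistic for the cluster term is

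LRT = 988 ln[(196F + 792)/988] − 196 ln F, for F > 1.

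The plan gives no cut-off. At an assumed 3.84 the term is dropped when F < 1.242. For slope ICC ρ, F is distributed as (1 + 4ρ)/(1 − ρ) times an F variable on 196 and 792 degrees of freedom, which gives the probability of dropping directly.

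**3. Type I error of the two-step rule.** The ML likelihood ratio test of treatment is then run with or without the cluster term. This was simulated with equal cluster sizes and no variance between sectors.

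| Slope ICC (assumed) | (1 + 4ρ)/(1 − ρ) | Dropped | Overall error under the rule | If always kept |
|---|---|---|---|---|
| 0.03 | 1.12/0.97 = 1.155 | 75% | 5.8% | 5.1% |
| 0.05 | 1.20/0.95 = 1.263 | 45% | 5.7-5.8% | 5.2% |
| 0.07 | 1.28/0.93 = 1.376 | 19% | 5.5% | 5.2% |
| 0.10 | 1.40/0.90 = 1.556 | 2.7% | 5.2% | 5.2% |

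In the trials where the term is dropped, the error is about 6.4% at ICC 0.03 and 7.5% at 0.05. The overall figure is lower because it averages over all trials. At 0.05, dropped trials contribute 0.45 × 7.5% = 3.4 points of the 5.8%.

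**4. Sensitivity to the cut-off.** At 2.71 (the 50:50 mixture reference) the overall error is 5.6%, 5.6%, 5.3% and 5.2% in the order of the table. If a term is kept only at p < 0.01 (200 clusters of 5), the highest error found is 6.3%, near ICC 0.05.

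**5. Three-wave check.** The full model at 0, 4 and 16 months, with assumed variance components and 250 variance fits per setting, gives 5.6-5.8% at slope ICC 0.03-0.05. The highest value is 6.0% if the subject slope may be dropped as well.

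**6. Sector.** Clusters were also stratified by sector, which is in no model and which makes the test conservative. The documents give neither the number of sectors nor their share of variance, so 15, 30 and 45 sectors were assumed. If a quarter of the cluster variance lies between sectors, the error under the rule is 5.2-5.6% at ICC 0.03-0.05 and 4.2-4.5% at 0.10. At a half share it is 4.7-5.3% and 3.6-3.9%. The gap to always keeping the term stays at about 0.5-0.8 points at ICC 0.03-0.05.

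The three-wave logistic and ZIP models were not simulated.

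**The case against.** The strongest reply is that the rule does no harm at the plan's own inputs. With 5 families and ICC 0.10 the error is 5.2% either way, and an excess appears only at slope ICCs that the documents do not give. That stands, with one reservation: the stated 0.10 is not tied to level or to change, so a smaller slope ICC cannot be excluded. It also stands that sector stratification can bring the absolute error back to 5% or below, so the table is the top of a range at its cut-off. Finally, always keeping the terms has its own departure from 5%, about 4.7% if cluster variance is zero (5.0% under the rule), though that errs on the safe side.

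Four stronger readings are tempting, and the documents do not support them.

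- **An error near 10%.** If the term were always omitted at ICC 0.10, the error would be 2[1 − Φ(1.96/√1.4)] = 9.8%. The rule omits it only after the LRT, which at that ICC happens in 2.7% of trials.
- **A plan that ignores clustering.** It does not: both cluster terms are in the starting model and the power calculation carries the ICC.
- **Selection on the treatment result.** The rule tests a variance, not B3.
- **A known, larger problem for binary or count outcomes.** The text carries the rule to binary outcomes. For ZIP this is a reasonable reading, but the sentence may describe model form only. Table 2 restricts partner-violence victimization ("Among cohabitating or married mothers only"), so fewer families per cluster will contribute, but no share is given and no error rate was computed for these models.

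**Conclusion.** The concern holds as a minor point. The plan states a rule under which the randomised unit can leave the treatment-effect model, and nothing elsewhere exempts it. For continuous outcomes the cost is about 0.5-0.7 percentage points of type I error at slope ICC 0.03-0.05, and nothing material at 0.10. This rests on an assumed cut-off of 3.84, equal clusters of 5 and assumed slope ICCs; the absolute error also assumes no variance between sectors. For binary outcomes the rule applies but the size is unknown. For ZIP both its reach and its size are open.

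**What to change.** State that the cluster random intercept and the cluster-by-time effect are exempt from the LRT dropping rule and stay in every treatment-effect model, whatever their estimated size. Limit model building to subject-level terms. If a cluster term cannot be estimated in a logistic or ZIP model, use a fallback named in advance that respects clusters: cluster-robust standard errors or a cluster-level analysis.

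This is a change to SAP wording only. Sample size, data collection and stated power are unaffected. The one downside is the slight conservatism noted above if there is truly no cluster variance.
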